2.2. Study Endpoints

2.2.1. Safety Endpoints

The following are the safety-related endpoints for Part B:

- Incidence of treatment-emergent adverse events (TEAEs) and serious adverse events (SAEs)
- Change from baseline in clinical laboratory evaluations
- Change from baseline in systemic lupus erythematosus (SLE) panel
- Change from baseline in vital signs
- Change from baseline in electrocardiogram (ECG) data
- Physical examination findings
- Incidence of infections of \geq Grade 3 severity (i.e., requiring intravenous [IV] antibiotics)

Details of the analysis of safety endpoints are described in [Section 8](#).

2.2.2. Efficacy Endpoints

The efficacy endpoints are the following parameters of disease activity:

- Hemoglobin
- Bilirubin (total)
- Lactate dehydrogenase (LDH)
- Haptoglobin
- Reticulocyte Count

- Transfusion requirements
- Incidence of solicited symptomatic anemia
- Incidence of thromboembolic events
- Incidence of hemolytic breakthrough
- Healthcare resource utilization parameters
- QOL assessments (FACIT-Fatigue, EQ-5D-5L, SF-12, PGIS, and PGIC)

Details of the analysis of efficacy endpoints are described in [Section 7](#).

2.2.3. Pharmacokinetic Endpoints

- Plasma concentrations of BIVV009

Details of the analysis of PK endpoints are described in [Section 9.1](#).

2.2.4. Pharmacodynamic Endpoints

- PD Primary Outcome Measures: Wieslab-CP
- Exploratory Complement System Measures: CH₅₀, Total C4, C1q, C1s

Details of the analysis of PD endpoints are described in [Section 9.2](#).

3. STUDY DESIGN

3.1. Overall Study Design and Plan

This open-label, single-arm study is designed to evaluate the efficacy, safety, and tolerability of BIVV009 in patients with the complement-mediated disorder, primary CAD, who have Hgb level ≤ 10 g/dL and a recent history of blood transfusion.

Following completion of dosing in the 6-month treatment period in Part A of the study, patients will continue to receive BIVV009 dosing during Part B, the long-term safety and durability of response extension phase. Part B will run for 1 year following LPO under Part A.

3.1.1. Study Sample

Patients in Part B will be a subset of the patients enrolled in Part A. All patients who complete Part A, including those receiving transfusions, will be eligible for Part B. Patients who withdraw from the study in Part A, including those who received prohibited concomitant medications, will not be eligible to participate in Part B. Subject inclusion and exclusion criteria for Part A can be found in Sections 5.1 and 5.2 of the protocol.

3.1.2. Treatment

Patients will be dosed with BIVV009 every 2 weeks, as in Part A. Should patients deviate from their scheduled dosing, a repeat loading dose may be required.

Patients requiring treatment with permitted concomitant medications and/or transfusions will not be discontinued from either Part A or Part B of the study. Patients in Part B will be transfused if his or her Hgb level meets either of the following criteria:

- Hgb is <9 g/dL and the patient is symptomatic, or
- Hgb is <7 g/dL and the patients is asymptomatic

A safety follow-up visit for collection of AE data, PK, PD, and antidrug antibodies (ADA) samples will be performed 9 weeks after administration of the last dose of study drug in patients who discontinue early. Samples for PK, PD, and ADA will also be collected from patients who experience a hemolytic breakthrough event.

The study will be complete 12 months following LPO for Part A. At this time, all ongoing patients receiving treatment in Part B will discontinue additional treatment visits and will follow-up with an EOS visit 9 weeks after last dose.

3.1.3. End of Study

The study will be considered complete 12 months following LPO from Part A. When this occurs, all ongoing patients in Part B will discontinue treatment and will return to the clinic for EOS assessments 9 weeks after last dose. End of study will occur when the last patient has had his or her last visit (Last Patient Last Visit).

3.2. Statistical Hypothesis

No formal statistical hypotheses will be tested. Analyses of efficacy endpoints will be primarily descriptive.

3.3. Sample Size Justification

No power and sample size analysis was conducted for Part B. Patients from Part A were enrolled into Part B following Part A EOT. The power and sample size calculation for Part A can be found in the Part A SAP.

3.4. Randomization and Blinding

This is an open-label study with no blinding or randomization.

3.5. Interim Analysis

For the purposes of regulatory submission, an interim analysis of safety and efficacy data will be performed for Part B after all patients have completed Part A, while Part B is still ongoing. Additional interim analyses of Part B data may be performed to obtain interim safety and efficacy results at the Sponsor's discretion for purposes of regulatory filings and requests, publications, or future planning. In general, these analyses will include safety and efficacy endpoints indicated in [Section 2.2.1](#) and [Section 2.2.2](#) through certain cutoff dates.

4. ANALYSIS POPULATIONS

The following analysis populations are defined for Part B of the study. For the remainder of the SAP, the term “subjects” will be used to refer to patients in the study to keep consistent with the term used within table, figure, and listing (TFL) displays.

In order to be consistent with Part B study objectives, the Per-Protocol Population described in the protocol was determined to have little utility and thus was not included in this SAP.

4.1. Full Analysis Set (FAS)

The Full Analysis Set is defined as all subjects who enroll into the Part B study and receive at least 1 dose (including partial dose) of study drug. The Full Analysis Set is synonymous with the Intent-to-Treat Population described in the protocol.

4.2. Safety Analysis Set

Subjects who receive at least 1 dose (including partial dose) of study drug in Part B will be included in the Safety Analysis Set. Note that Safety Analysis Set is the same as the Full Analysis Set in this study.

4.3. PK Analysis Set

Subjects who received at least 1 dose of study drug in Part B and have evaluable PK concentrations will be included in PK analysis set.

4.4. PD Analysis Set

Subjects who received at least 1 dose of study drug in Part B and have at least 1 evaluable PD sample will be included in the PD analysis set.

5. DEFINITIONS AND DATA HANDLING

Statistical analysis will be performed by Bioverativ, using SAS[®] version 9.4 or higher and, where appropriate, additional validated software.

5.1. General Principles

Safety, efficacy, and PK/PD data will be summarized using standard summary statistics for continuous, categorical, and time-to-event data. Data will be summarized for the populations defined. All efficacy and safety data, including derived variables, will be listed for all visits.

No statistical hypothesis testing is planned.

5.1.1. Definitions

Study Day

Study Day is defined as days relative to the date of first dose of BIVV009 in Part A, Day 0. The start/stop day of events will be calculated as (date of event – date of Day 0 +1).

Incomplete dates will be imputed for the calculation of study days, unless specified otherwise:

- If missing day only, the start date will be imputed as the first day of the month, while the end date will be imputed as the last day of the month;
- If missing day and month, the start date will be imputed as the first day of the year, while the end date will be imputed as the last day of the year;

Baseline

Baseline is defined as the last non-missing value prior to the first administration of study drug in Part A. If a transfusion occurred during the screening period, the baseline measure must be at least 7 days after the transfusion.

Study Treatment Period

For subjects who enroll into Part B, the Part A study treatment period starts at the date of first study drug administration and ends at the date of Week 26 visit. The Part B study treatment period starts following completion of Part A (ie, immediately following Week 26 visit) and ends at the ET/EOS/Safety follow-up visit, which is 9 weeks after each subjects' last dose.

The Combined Study Period includes all visits in Part A and Part B and will be utilized for a subset of analyses in order to support regulatory submissions and/or publications.

Visit Windows

Analysis by study visit will utilize the data recorded on the corresponding nominal visit from electronic Case Report Forms (eCRFs). In case of missing data/assessments for a visit, data from an unscheduled visit, or ET/Safety Follow-up Visit will be used, if the Study Day of such a

visit fits in the analytic window defined below. If multiple values are identified within the analytic window, the one closest to the target study day will be used.

- Starting at Week 27 and every 2 weeks thereafter, analytic visit windows in Part B will be -6 days to +7 days from the Target Study Days of the protocol-defined visits. An example of the first few visits in Part B can be seen in Table 1, below.

Table 1: Analytic Visit Windows

Visit	Target Study Day	Analytic Visit Window (Study Day)
Week 27	189	183-196
Week 29	203	197-210
Week 31	217	211-224
Week 33	231	225-238
Etc.		

Solicited Symptomatic Anemia

Refer to the Part A SAP for definitions regarding the severity of CAD symptomatic anemia.

Thromboembolic Events

Thromboembolic events prior to Part A study entry are recorded as medical history in the eCRFs, while thromboembolic events on Part A and Part B study are captured as adverse events. Both medical history and adverse events will be coded according to Medical Dictionary for Regulatory Activities (MedDRA) v20.1 or higher.

All thromboembolic events reported (as AEs) will be reviewed and determined by internal medical staff via medical adjudication.

Hemolytic Breakthrough

Hemolytic breakthrough at any visit is defined as

- A decrease of 2 g/dL or more in Hgb from the last scheduled visit, and
- One of the followings:
 - An increase of LDH from the last scheduled visit, or
 - An increase of bilirubin from the last scheduled visit, or
 - A decrease in haptoglobin from the last scheduled visit.

Protocol Prohibited CAD Medications

The following concomitant medications are prohibited during the study treatment period:

- Rituximab alone or as part of combination therapy
- Cytotoxic drugs (such as fludarabine, bendamustine, ibrutinib, cyclophosphamide)
- Other investigational drug

The eCRF questionnaire “Did the subject receive any prohibited medications since the last visit?” will be used to account for protocol-prohibited CAD medication use. Medical review for the list of protocol-prohibited CAD medications will be reconciled with the eCRF questionnaire.

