7.2. Analysis of Efficacy Endpoints (Part B Study Period)

All analyses described below will be performed on the Part B Study Period, starting at Week 27.

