7.2.2. Categorical Endpoints

The categorical endpoints include:

- Incidence of solicited symptomatic anemia
- Incidence of other CAD-related symptoms

The above endpoints will be summarized by visit descriptively using the FAS and will be based on the observed data starting at Week 27, continuing through the Week 77 visit. Baseline summaries will be included for comparative purposes. For patients with more than 12 months of follow-up in Part B, observed data at the Week 79 visit and beyond will be provided in the listings.

Additionally, the following endpoints will be summarized using all data in Part B (including data from the Week 79 visit and beyond):

- Incidence of thromboembolic events

- Incidence of hemolytic breakthrough

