7.3.1. Continuous Endpoints

The continuous endpoints include:

- Hemoglobin
- Bilirubin (total)

The above endpoints will be summarized by visit, starting at Baseline/Day 0 and will continue through the Week 77 visit. Summary tables will include change from baseline and individual summary statistics will follow those presented in [Section 5.2.1](#). For patients with more than 12 months of follow-up in Part B, all endpoints at the Week 79 visit and beyond will be provided in a data listing.

Line plots of mean hemoglobin and bilirubin over time, starting at Baseline/Day 0, will be presented. Additionally, a line plot of mean change from baseline in hemoglobin over time, starting at Baseline/Day 0, will be presented.

Additionally, the following continuous endpoints will be summarized by Study Period using FAS as specified in [Section 5.2.1](#):

- Number of transfusions and total transfusion units
- Annualized number of transfusions and annualized transfusion units

For number of transfusions and total transfusion units, data up to Week 77 will be considered, for both Part B and Combined Study Period summaries. All data after Week 77 will be provided in the listing.

For annualized number of transfusions and annualized transfusion units, all Part B data will be considered. Annualized values will be calculated for each patient using the following formula:

$$\text{Annualized value} = \frac{\text{Number of events during the Study Period}}{\text{Total number of days during the Study Period}} \times 365.25$$

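### Part B hemolytic breakthrough incidence and annualised transfusion rates include the 9 weeks after last dose, with no on-treatment result beside them

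*SAP*

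**What the plan says.** **Period.** Part B SAP 5.1.1 opens the Part B study treatment period right after the Week 26 visit "and ends at the ET/EOS/Safety follow-up visit, which is 9 weeks after each" subject's last dose. The Combined Study Period covers all Part A and Part B visits, so it contains the same tail.

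**Who has off-drug time.** At study end, "all ongoing patients in Part B will discontinue treatment and will return to the clinic for EOS assessments 9 weeks after last dose" (Part B SAP 3.1.3). Early discontinuers have the same 9-week visit.

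**Breakthrough.** "Incidence of hemolytic breakthrough" is a Part B efficacy endpoint (2.2.2). Section 5.1.1 says "Hemolytic breakthrough at any visit is defined as" a hemoglobin fall of at least 2 g/dL since the last scheduled visit with a supporting change in LDH, bilirubin or haptoglobin. Last dose is not mentioned. On analysis, "All analyses described below will be performed on the Part B Study Period, starting at Week 27" (7.2), and 7.2.2 includes breakthrough among the endpoints that use all Part B data, without the Week 77 limit.

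**Transfusions.** "For annualized number of transfusions and annualized transfusion units, all Part B data will be considered" (7.3.1). The formula divides "Number of events during the Study Period" by the total days in that period and multiplies by 365.25.

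**The one rule tied to last dose.** Section 6.5.1 computes exposure duration in Part B as last dose − Part B start + 15 days. It is not applied to the two outputs above.

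**The concern.** The secondary objective of Part B (SAP 2.1.2) is durability of response while patients are on long-term treatment. The two outputs named here bear directly on it, but as specified they combine time on drug with time after stopping.

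The documents give reason to expect events in that later time. Protocol 2.2.2 reports that hemolytic anemia relapsed on washout in Phase 1b. Protocol 6.1.7 schedules hematology, chemistry and transfusion recording at the 9-week visit, and asks for samples if breakthrough occurs during follow-up. At that visit the comparator for breakthrough is the last scheduled visit, which is an on-drug value, and the SAP definition sets no limit on how fast hemoglobin must fall. A decline caused by stopping the drug can therefore count as a failure of durability.

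The distortion runs both ways. Off-drug events push the figures up, and off-drug days without events pull the annualised rates down. A reader of the summary table could not tell which had happened. The listings would let someone find the events but would not change the summary figures.

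**Working it through.** The SAP states no breakthrough incidence or annualised rate, so there is no figure to reproduce. The check applies the SAP's own formula to two period ends.

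**Inputs**
- Dosing interval: 14 days (Part B SAP 3.1.2).
- Period end: 63 days after last dose (5.1.1).
- Exposure convention: last dose − start + 15 days, that is, to 14 days after last dose, counted inclusively (6.5.1).
- Annualised value = events ÷ days in period × 365.25 (7.3.1).
- D, days from Part B start to last dose: assumed 364, 728 and 1092 (52, 104 and 156 weeks). 52 weeks is about the shortest dosing time for a completer under the SAP's 12 months after last patient out. 104 and 156 weeks match the 2 to 3 years in protocol 4.4.
- Part B N: not given. About 20 patients are planned for the trial (protocol 7.10); 15 to 20 is assumed.

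**Step 1: extra days.** 63 − 14 = 49 days per patient who reaches the visit.

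**Step 2: dilution by event-free follow-up.**

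| Part B dosing | D + 15 (to last dose + 14) | D + 64 (to 9-week visit) | 49 ÷ (D + 64) |
|---|---|---|---|
| 52 weeks | 379 | 428 | 11.4% |
| 104 weeks | 743 | 792 | 6.2% |
| 156 weeks | 1107 | 1156 | 4.2% |

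For example, two on-treatment transfusions in 52 weeks give 2 × 365.25 ÷ 379 = 1.93 per year to last dose + 14, but 2 × 365.25 ÷ 428 = 1.71 per year to the 9-week visit. In the Combined Study Period the denominator also holds Part A, so the share is smaller.

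**Step 3: inflation by an off-drug event.** Take a patient with no on-treatment transfusion and one in days 15 to 63 after last dose:
- 52 weeks: 365.25 ÷ 428 = 0.85 per year
- 104 weeks: 365.25 ÷ 792 = 0.46 per year
- 156 weeks: 365.25 ÷ 1156 = 0.32 per year

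With the earlier cut each is 0. These are single-patient values. With N = 20, one such patient moves the group mean by 0.85 ÷ 20 = 0.04, 0.46 ÷ 20 = 0.02 or 0.32 ÷ 20 = 0.02 per year.

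**Step 4: breakthrough.** Each patient who meets the definition only after treatment adds 1/20 = 5.0 to 1/15 = 6.7 percentage points.

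**Step 5: which other summaries are exposed.** By-visit hemoglobin, bilirubin, LDH, haptoglobin, reticulocytes and patient-reported outcomes, and the non-annualised transfusion counts and units, stop at Week 77 (7.2.1, 7.2.3, 7.3.1). Displays of time to first transfusion stop at Study Day 540 (7.3.2). A completer dosed for 52 weeks from Week 27 is still on drug at Week 77, so follow-up does not enter these for completers.

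**Step 6: early discontinuers and visit windows.** Section 5.1.1 lets an ET value fill a missing visit if it falls in that visit's window. The windows are contiguous (−6 to +7 days around 14-day targets). By the pattern of Table 1, Week 77 has target 7 × 77 = 539 and window 533 to 546. After a last dose at Week 67 (7 × 67 = day 469), a visit 61 to 65 days later falls on days 530 to 534, inside a window at or before Week 77. An off-drug value can therefore stand in for a dosing visit in a by-visit efficacy summary.

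**The case against.** The strongest reply is that this is a choice of period, not a mistake. Part B tests no hypothesis (SAP 3.2), counting everything to the end of follow-up is an accepted convention, and for events it works against the drug. The protocol plans to sample breakthrough in follow-up, so those events should not be lost. Nor is last dose + 14 days better founded as an end of effect: the documents give no half-life or washout time, and protocol 2.1 and 2.2.3 tie inhibition to concentration rather than to days since dosing. All of this stands. It is why the on-treatment result belongs beside the all-Part-B result and should not replace it. It does not remove the need for that result, because dilution of the annualised rates favours the drug and the objective concerns time on treatment.

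Three stronger readings are tempting, and the documents do not support them.

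- A reader might infer that the annualised formula has two equally good readings, ending at the 9-week visit or at last dose + 14 days. Section 7.3.1 says all Part B data and 5.1.1 gives the period's end, so the 9-week reading is much the better supported. Section 6.5.1 is an exposure calculation, and an exposure duration that differs from an observation period is not an error. A cross-reference in 7.3.1 would still help.
- A reader might infer that every completer adds nine off-drug weeks to every analysis. Beyond one dosing interval the excess is seven weeks (49 days). At an interim analysis (3.5), patients still being dosed add none.
- A reader might infer that the durability evidence as a whole is contaminated. The Week 77 and Study Day 540 limits keep completers' follow-up out of most of it.

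**Conclusion.** The concern holds for two outputs: hemolytic breakthrough incidence, and annualised transfusions and units. Followed as written, the final Part B analysis mixes 49 days per patient beyond one dosing interval into summaries that are meant to show durability on treatment. An on-treatment annualised rate is diluted by 4.2% to 6.2% at 3 to 2 years of Part B dosing, and by 11.4% at 1 year. Each patient whose only breakthrough comes after treatment adds 5.0 to 6.7 percentage points, if N is 20 to 15.

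The size rests on assumed dosing durations, an assumed N and assumed events. The documents do not give a post-treatment relapse rate, so the number of patients affected is unknown. No error rate or power is involved. The matter is modest but worth correcting before the final analysis, because it affects how two durability figures are read and costs little. The visit-window issue is a minor related point for early discontinuers only.

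**What to change.** In the Part B SAP:

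1. Define an on-treatment period from Part B start to last dose + 14 days, the convention already used for exposure in 6.5.1.
2. For breakthrough incidence and for annualised transfusions and units, report the on-treatment result beside the all-Part-B result. For the rates, apply the same cut to numerator and denominator.
3. Tabulate events from the cut to the 9-week visit separately, so that no follow-up event is lost and events soon after stopping stay visible.
4. State in 7.3.1 which period each annualised rate uses.
5. In by-visit efficacy summaries, do not fill a missing dosing-visit window with an ET value taken after the cut (5.1.1).
6. Leave adverse event follow-up at 9 weeks.

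The cost is SAP wording, one period flag and one extra descriptive table; no new data are needed. The downside is that the cut is a convention and not a demonstrated end of drug effect. The separate follow-up table makes that visible.

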- r* During Part B, ADA samples will be collected at predose at 3-month intervals during the 1st year of treatment in Part B and then at 6-month intervals and at safety follow up visit 9 weeks after last dose. Samples will also be collected if a patient experiences a hematologic breakthrough event or withdraws from the study early.
- s* SLE panel will be performed every 6 months in Part-B of the study.
- t* In Part B, hematology and clinical chemistry panels to be performed every 2 weeks after Week 25 and up to Week 79. For the remainder of Part B after Week 79, hematology and clinical chemistry panels to be performed every 4 weeks.
- u* To be performed at 3-month intervals during the 1st year of treatment in Part B, and then at 6-month intervals.

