- o In Part B, hematology and clinical chemistry panels to be performed every 2 weeks after Week 25 and up to Week 79 (every 4 weeks in patients within the home infusion scheme). For the remainder of Part B after Week 79, hematology and clinical chemistry panels to be performed every 4 weeks.
- p SLE panel testing should occur every 6 months at on site visits in Part B.

Section 2.2 (Background and Study Rationale)

Patients with CAgD are often elderly and/or have numerous co-morbidities affecting their mobility. Moreover, clinical centers specialized in the management of CAgD are infrequent and may be located far from patients' home. Consequently, some patients may find the option of home infusions with drug against CAgD, beneficial. To this end a group of patients at preselected sites/countries will be offered the possibility of home infusions during Part B, assisted by trained health care professional.

Section 2.2.4 (Potential Risks and Benefits)

Home infusions with the study drug will be proposed to a number of patients in countries pre-selected to participate in home infusion. Home infusions will be assisted by a trained healthcare professional, and will concern patients who express such wish, after having been qualified by the Investigator and no sooner than after Week 41 (Day 287) and without evidence of intolerance of the study drug as determined by the Investigator. No new risks related to home infusions are anticipated. Like with office visits, medications such as epinephrine and diphenhydramine, and additional emergency equipment will be available in case an allergic reaction or anaphylaxis occurs during home infusion. Professional healthcare caregiver will be qualified to detect and treat allergic reactions and anaphylaxis. The alternating schedule of home infusion visits and office visits every 4 weeks each may be found convenient by patients as less travels to the study site will be necessary.

Section 3.5 (Exploratory objective [Part B])

- To describe the safety and patient satisfaction with the convenience of home infusions with BIVV009 in a subset of patients in the US, the Netherlands, Norway, France, Italy, Austria, Germany, and Spain.

Section 4.1 (Study Design: Part-B)

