8.2.1.1. Change from Baseline

Hematology and chemistry results at baseline and Part B post-baseline visits, along with change from baseline, will be summarized with descriptive statistics. These by-visit summaries will be presented through the end of Part B.

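### Part B safety lab tables keep 2-week windows after Week 79, when panels become 4-weekly, and the fill rule lets unscheduled or post-treatment values occupy rows with no scheduled draw

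*SAP*

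**What the plan says.** **Windows.** Part B SAP 5.1.1 (Visit Windows) reads: "Starting at Week 27 and every 2 weeks thereafter, analytic visit windows in Part B will be -6 days to +7 days", counted from the target day of each visit. No later change of grid is given.

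**Fill rule.** The same section adds: "In case of missing data/assessments for a visit, data from an unscheduled visit, or ET/Safety Follow-up Visit will be used", provided the value falls in the window. If several values fall in the window, the one closest to target is taken. The rule does not separate a panel that was missed from one that was never scheduled.

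**Sampling.** Protocol Table 3, footnote t, has "hematology and clinical chemistry panels to be performed every 2 weeks after Week 25 and up to Week 79", and then "For the remainder of Part B after Week 79, hematology and clinical chemistry panels to be performed every 4 weeks". Protocol 6.1.5.1 and 6.1.5.2 agree. Appendix J, Table 4, footnote o, makes the panels before Week 79 "every 4 weeks in patients within the home infusion scheme". Appendix J also rules out blood sampling at home visits.

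**Output.** Part B SAP 8.2.1.1 says of hematology and chemistry: "These by-visit summaries will be presented through the end of Part B". Section 8.2.1 includes hemoglobin and total bilirubin among these measurements. The efficacy by-visit tables for LDH, haptoglobin, reticulocytes, hemoglobin and bilirubin (7.2.1 and 7.3.1) end at Week 77, with later values listed only.

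**The concern.** A by-visit table is read down the column as a time trend, which assumes that neighbouring rows describe much the same patients under much the same sampling. After Week 79 that fails in the safety lab tables. One row holds the scheduled panels. The next has no scheduled panel for site patients, and the fill rule invites whatever else falls in the window.

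The candidates are not a neutral sample:

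- Protocol 6.6 allows safety evaluations to be repeated as medical management requires.
- The ET/EOS/follow-up panel is drawn 9 weeks after the last dose (Protocol 6.1.7), and Protocol 2.2.2 reports relapse of hemolytic anemia on washout.

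A row made of a few such values could be taken for a late fall in hemoglobin or rise in bilirubin under treatment. Long-term safety is the primary objective of Part B and durability of response the secondary one, so late trends in these two parameters will be looked at.

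**Working it through.** This is schedule arithmetic; no power formula bears on it.

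**1. Reproduce the plan's windows.** Target = 7 × week; window = target − 6 to target + 7.

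| Week | Target | Window | Part B SAP Table 1 |
|---|---|---|---|
| 27 | 189 | 183–196 | same |
| 29 | 203 | 197–210 | same |
| 31 | 217 | 211–224 | same |
| 33 | 231 | 225–238 | same |

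All four reproduce. The 14-day windows are contiguous, so every value falls in some row.

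**2. Length of Part B.** Protocol 4.4 gives 2 to 3 years of Part B dosing per patient from Week 27: 27 + 104 = Week 131, and 27 + 156 = Week 183.

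**3. Rows after the schedule change.** I take the 4-week cycle as starting at Week 79 (Protocol 6.1.5.2), so panels fall at Weeks 79, 83, 87 and so on.

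| End | 2-week rows from Week 79 | Rows with a scheduled panel | Rows without |
|---|---|---|---|
| Week 131 | (131 − 79)/2 + 1 = 27 | (131 − 79)/4 + 1 = 14 | 13 |
| Week 183 | (183 − 79)/2 + 1 = 53 | (183 − 79)/4 + 1 = 27 | 26 |

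**4. What can enter a row without a scheduled panel.**

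- Home-infusion patients whose office visits are out of phase with the site cycle. Phases can differ because a 3-month assessment visit displaces a home visit and restarts the alternation (Appendix J).
- Unscheduled values. Protocol 7.1 reserves lab endpoints for central-laboratory results, so local values taken for management should not ordinarily enter.
- ET/follow-up values from 9 weeks after the last dose. These can fall in either kind of row, depending on the date of the last dose.

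With no home-infusion patients, such a row is empty apart from the last two sources.

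**5. Before Week 79.** Site patients are sampled every 2 weeks, so the grid fits them. Home infusion may start only after Week 41 (Day 287 = 7 × 41; Protocol 2.2.4), so Week 43 is the first possible row. Weeks 43 to 77 give (77 − 43)/2 + 1 = 18 of the 26 efficacy rows from Week 27 to Week 77. A patient starting home infusion at Week 43 has no scheduled panel in 9 of the 18 with strict alternation. If 3-month visits fall at Weeks 51, 65 and 77 (assumed), the count is 8. The documents do not say how many patients use home infusion, or how many had yet to reach Week 77 when it was introduced.

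**The case against.** **The efficacy tables largely escape.** They end at Week 77, just before sampling changes. This stands. A reader might infer that the durability summaries themselves are distorted after Week 79; the documents do not support that. They would be reached only if the optional summaries beyond 12 months (Part B SAP 5.1.3) were produced. The hemoglobin and bilirubin plots in 7.3.1 have no stated end week, but nothing says they go past Week 77.

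**The central-laboratory rule keeps out most urgent values.** This largely stands. Unscheduled central samples and follow-up panels remain. Protocol 6.3.7 also qualifies the use of central results for efficacy by whether they were collected and are available.

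**The table shows its own weakness.** Part B tests no hypothesis (3.2), continuous summaries print n (5.2.1), attendance by visit is tabulated and all values are listed. This stands as a limit on the harm. It does not justify rows that the schedule cannot fill.

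**A sensible programmer would not call a never-scheduled panel missing.** Possibly, but the rule as written does not say so, and Protocol section 7 gives the SAP precedence on analysis.

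**The cause is an outdated SAP.** The Part B SAP still describes a Part B of 1 year after last patient out and does not mention home infusion. That is probably the origin, and bringing it into line with amendment 06 is the occasion to change the windows.

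**Conclusion.** The concern holds for the safety by-visit hematology and chemistry tables after Week 79. There, 13 rows (Part B ending near Week 131) to 26 rows (near Week 183), about half of those from Week 79 on, have no scheduled draw for site patients, and the fill rule allows selected values into them. The counts rest on the protocol's 2 to 3 years of Part B dosing and on a 4-week cycle starting at Week 79.

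Before Week 79 the mismatch concerns home-infusion patients only, from Week 43 at the earliest. With their number unknown, its effect on the efficacy tables may be small or nil.

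A reader might go on to infer a hemoglobin shift of some stated size, or a regular saw-tooth. The documents support neither. They give no home-infusion uptake and no hemoglobin difference between home and site patients. The home-infusion criteria contain no hemoglobin threshold, and mixed phases would blunt any alternation.

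The consequence is for how late trends are read. No test or success criterion depends on it. The point is worth acting on because the remedy is cheap.

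**What to change.** In Part B SAP 5.1.1:

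1. **After Week 79**, present by-visit hematology and chemistry only on the 4-week panel schedule, with 28-day windows and the scheduled on-site value preferred. On Table 1's day count, Week 83 has target 7 × 83 = 581 and window 581 − 13 to 581 + 14 = 568–595. Week 79 (target 553) would then run from 547 to 567 so that no gap is left. This gives 14 rows to Week 131 or 27 to Week 183, each with a scheduled panel. A home-infusion patient has about one scheduled sample per window, whatever the phase.
2. **Throughout Part B**, state that an unscheduled or ET/follow-up value may not fill a window in which that patient had no scheduled panel. Keep those values in the listings and in the minimum/maximum shift tables, which already take unscheduled data (8.2.1.2).
3. **Keep the 2-week grid** through Week 77 for site patients, and throughout for items collected at every visit, such as solicited symptomatic anemia.

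Moving everyone to a 4-week grid from Week 41 is not needed. It would drop about half of the scheduled values of site-only patients up to Week 77 for the sake of an unknown number of home-infusion patients.

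The cost is SAP wording, window programming and fewer rows after Week 79. Data collection does not change.
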